6.5 Timing of Dose Administration

Trial treatment should be administered on Day 1 of each cycle after all procedures/assessments have been completed as detailed on the Trial Flow Chart (Section 8.0). Trial treatment may be administered up to 3 days before or after the scheduled Day 1 of each cycle due to administrative reasons.

All trial treatments will be administered on an outpatient basis.

Pembrolizumab 200 mg will be administered as a 30 minute IV infusion every 3 weeks. Sites should make every effort to target infusion timing to be as close to 30 minutes as possible. However, given the variability of infusion pumps from site to site, a window of -5 minutes and +10 minutes is permitted (i.e., infusion time is 30 minutes: -5 min/+10 min).

The Package Insert contains specific instructions for the preparation of the pembrolizumab infusion fluid and administration of infusion solution.

6.6 Trial Blinding/Masking

This is an open-label trial; therefore, the Sponsor, investigator and subject will know the treatment administered.

6.7 Concomitant Medications/Vaccinations (allowed & prohibited)

Medications or vaccinations specifically prohibited in the exclusion criteria are not allowed during the ongoing trial. If there is a clinical indication for one of these or other medications or vaccinations specifically prohibited during the trial, discontinuation from trial therapy or vaccination may be required. The investigator should discuss any questions regarding this with the Merck Clinical team. The final decision on any supportive therapy or vaccination rests with the investigator and/or the subject's primary physician.

6.7.1 Acceptable Concomitant Medications

All treatments that the investigator considers necessary for a subject's welfare may be administered at the discretion of the investigator in keeping with the community standards of medical care. All concomitant medication will be recorded on the case report form (CRF) including all prescription, over-the-counter (OTC), herbal supplements, and IV medications and fluids. If changes occur during the trial period, documentation of drug dosage, frequency, route, and date may also be included on the case report form (CRF).

All concomitant medications received within 28 days before the first dose of trial treatment and 30 days after the last dose of trial treatment should be recorded. Concomitant medications administered after 30 days after the last dose of trial treatment should be recorded for SAEs and ECIs as defined in Section 11.

6.7.2 Prohibited Concomitant Medications

Subjects are prohibited from receiving the following therapies during the Screening and Treatment Phase (including retreatment for post-complete response relapse) of this trial:

- Antineoplastic systemic chemotherapy or biological therapy
- Immunotherapy not specified in this protocol
- Chemotherapy not specified in this protocol
- Investigational agents other than pembrolizumab
- Radiation therapy
 - Note: Radiation therapy to a symptomatic solitary lesion or to the brain may be allowed at the investigator's discretion.
- Live vaccines within 30 days prior to the first dose of trial treatment and while participating in the trial. Examples of live vaccines include, but are not limited to, the following: measles, mumps, rubella, varicella/zoster, yellow fever, rabies, BCG, and typhoid vaccine.
- Systemic glucocorticoids for any purpose other than to modulate symptoms from an event of clinical interest or suspected immunologic etiology. The use of physiologic doses of corticosteroids may be approved after consultation with the Sponsor.

Subjects who, in the assessment by the investigator, require the use of any of the aforementioned treatments for clinical management should be removed from the trial. Subjects may receive other medications that the investigator deems to be medically necessary.

The Exclusion Criteria describes other medications which are prohibited in this trial.

There are no prohibited therapies during the Post-Treatment Follow-up Phase.

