6.2 Subject Exclusion Criteria

The subject must be excluded from participating in the trial if the subject:

1. Is currently participating and receiving study therapy or has participated in a study of an investigational agent and received study therapy, or used an investigational device within 4 weeks of the first dose of treatment.
2. Has a diagnosis of immunodeficiency or is receiving systemic steroid therapy or any other form of immunosuppressive therapy within 7 days prior to the first dose of trial treatment.
3. Has a known history of active TB (Bacillus Tuberculosis)
4. Hypersensitivity to pembrolizumab or any of its excipients.
5. Has had a prior anti-cancer monoclonal antibody (mAb) within 4 weeks prior to study Day 1 or who has not recovered (i.e., \leq Grade 1 or at baseline) from adverse events due to agents administered more than 4 weeks earlier.
6. Has had prior chemotherapy, targeted small molecule therapy, or radiation therapy within 2 weeks prior to study Day 1 or who has not recovered (i.e., \leq Grade 1 or at baseline) from adverse events due to a previously administered agent.
 - Note: Subjects with \leq Grade 2 neuropathy are an exception to this criterion and may qualify for the study.
 - Note: If subject received major surgery, they must have recovered adequately from the toxicity and/or complications from the intervention prior to starting therapy.
7. Has a known additional malignancy that is progressing or requires active treatment. Exceptions include basal cell carcinoma of the skin or squamous cell carcinoma of the skin that has undergone potentially curative therapy or in situ cervical cancer.

8. Has known active central nervous system (CNS) metastases and/or carcinomatous meningitis. Subjects with previously treated brain metastases may participate provided they are stable (without evidence of progression by imaging for at least four weeks prior to the first dose of trial treatment and any neurologic symptoms have returned to baseline), have no evidence of new or enlarging brain metastases, and are not using steroids for at least 7 days prior to trial treatment. This exception does not include carcinomatous meningitis which is excluded regardless of clinical stability.

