9. Has active autoimmune disease that has required systemic treatment in the past 2 years (i.e. with use of disease modifying agents, corticosteroids or immunosuppressive drugs). Replacement therapy (e.g., thyroxine, insulin, or physiologic corticosteroid replacement therapy for adrenal or pituitary insufficiency, etc.) is not considered a form of systemic treatment.
10. Has immunohistochemically proven mismatch repair deficient cancer (this test is standard in our center for colorectal and endometrial cancer patients, and documentation will be required to be negative to accept outside referrals with colorectal or endometrial cancer for this trial).
11. Has a history of (non-infectious) pneumonitis that required steroids or current pneumonitis
12. Evidence of interstitial lung disease.
13. Has an active infection requiring systemic therapy.
14. Has a history or current evidence of any condition, therapy, or laboratory abnormality that might confound the results of the trial, interfere with the subject's participation for the full duration of the trial, or is not in the best interest of the subject to participate, in the opinion of the treating investigator.
15. Has known psychiatric or substance abuse disorders that would interfere with cooperation with the requirements of the trial.
16. Is pregnant or breastfeeding, or expecting to conceive or father children within the projected duration of the trial, starting with the pre-screening or screening visit through 120 days after the last dose of trial treatment.
17. Has received prior therapy with an anti-PD-1, anti-PD-L1, or anti-PD-L2 agent.
18. Has a known history of Human Immunodeficiency Virus (HIV) (HIV 1/2 antibodies).
19. Has known active Hepatitis B (e.g., HBsAg reactive) or Hepatitis C (e.g., HCV RNA [qualitative] is detected).
20. Has received a live vaccine within 30 days of planned start of study therapy.

Note: Seasonal influenza vaccines for injection are generally inactivated flu vaccines and are allowed; however intranasal influenza vaccines (e.g., Flu-Mist®) are live attenuated vaccines, and are not allowed.

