7.2 Subject Replacement Strategy

We anticipate enrollment of 39 patients for which tumor and toxicity assessments following pembrolizumab administration can be made. We will replace patients enrolled for which clinical trial discontinuation was performed prior to any administration of pembrolizumab or those for which pembrolizumab is discontinued due to acute hypersensitivity reactions during the first administration of pembrolizumab. An attempt will be made to assess tumor response in all enrolled patients as specified in the protocol. However, patients experiencing clinical deterioration after two doses of pembrolizumab, will be considered treatment failures and will count as tumor progression. These patients will not be replaced.

We are also expecting that 30% of the patients enrolled will be negative on the FATS1 assay, which will be conducted in batched analyses.

See section 6.1.1 and 12.0.1 for expansion cohort.

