9.0.2.6 Tumor Imaging and Assessment of Disease

Tumor assessments will be performed by computer tomography (CT) or Magnetic Resonance Imaging (MRI). Measurable disease will be required by computer tomography or MRI examination obtained within 21 days of first dose of therapy. Scans obtained prior to consenting will be allowed, as long as performed within 21 days of study initiation. CT Scans or MRI's will be repeated every 2 cycles (3 weeks cycles); that is before every third dose of pembrolizumab in order to assess response to therapy. [Tumor imaging will only be required every 12 weeks for patients that have been on treatment for more than 1 year.](#) Immune-related Response Criteria (irRC) [30] will be utilized for assessment of response to therapy.

Systematic criteria designated immune-related response criteria were defined based on four distinct response patterns seen after administration of ipilimumab: (a) shrinkage in baseline lesions, without new lesions; (b) durable stable disease (in some patients followed by a slow, steady decline in total tumor burden); (c) response after an increase in total tumor burden; and (d) response in the presence of new lesions. These four patterns were associated with favorable survival [30].

For the irRC index and measurable new lesions are taken into account to calculate evolving tumor burden. At baseline, the sum of the products of the two largest perpendicular diameters (SPD) of all index lesions (five lesions per organ, up to 10 visceral lesions) is calculated. At each subsequent tumor assessment, the SPD of the index lesions and of new, measurable lesions (up to 5 new lesions per organ; 10 visceral lesions) are added together to provide the total tumor burden. A comparison of the use of SPD in WHO criteria versus the use of tumor burden in irRC is presented in Table 8.

Table 7. Comparison between WHO criteria and the irRC

WHO		irRC
New, measurable lesions	Always represent PD	Incorporated into tumor burden.
New, nonmeasurable lesions	Always represent PD	Do not define progression (but preclude irCR)

Non-index lesions	Changes contribute to defining best overall response	Contribute to defining irCR (complete disappearance required)
CR	Disappearance of all lesions in two consecutive observations not less than 4 weeks apart.	Disappearance of all lesions in two consecutive observations not less than 4 weeks apart.

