9.0.2.7 Overall response using the irRC

- **irCR:** Complete disappearance of all lesions (whether measurable or not, and no new lesions) confirmed by a repeat, consecutive assessment no less than 4 weeks from the date first documented.
- **Ir PR:** Decrease in tumor burden $\geq 50\%$ relative to baseline confirmed by a consecutive assessment at least 4 weeks after first documentation.
- **irSD:** Not meeting criteria for irCR or irPR, in absence of irPD.
- **irPD:** Increase in tumor burden $\geq 25\%$ relative to nadir (minimum recorded tumor burden) confirmed by a repeat, consecutive assessment no less than 4 weeks from the date first documented.

Major differences with other tumor response criteria include: PR or SD in the presence of new lesions, as long as they met the respective threshold of response based on total differences in tumor burden; an SD does not require confirmation; however PD requires confirmation by another scan at least 4 weeks apart in the absence of rapid clinical deterioration.

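### Radiation to a symptomatic solitary lesion may be allowed during treatment, and no rule stops the resulting shrinkage from being scored as an irPR and counted toward the 2-of-20 and 4-of-39 rules

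*Combined protocol and SAP*

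**What the plan says.** Section 6.7.2 lists radiation among the therapies prohibited during the Screening and Treatment Phase. A note under that item says: "Radiation therapy to a symptomatic solitary lesion or to the brain may be allowed", at the investigator's discretion. The list closes by saying that subjects who "require the use of any of the aforementioned treatments for clinical management should be removed from the trial".

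Section 9.0.2.6 sets baseline tumor burden as the SPD of all index lesions. Follow-up burden is built the same way: "At each subsequent tumor assessment, the SPD of the index lesions and of new, measurable lesions" are added together. Section 9.0.2.7 defines irPR as a fall in burden of at least 50% "relative to baseline confirmed by a consecutive assessment at least 4 weeks after first documentation". Neither section mentions irradiated lesions.

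Section 12.0 makes the immune-related objective response rate the primary endpoint. The trial continues if at least 2 of the first 20 evaluable patients respond, and the null (5% or less) is rejected with at least 4 responses in 39.

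Three other texts bear on the point:

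- **Baseline scan (9.0.2.6):** "Scans obtained prior to consenting will be allowed, as long as performed within 21 days of study initiation".
- **Exclusion 6 (6.2):** excludes a patient who "Has had prior chemotherapy, targeted small molecule therapy, or radiation therapy within 2 weeks prior to study Day 1".
- **Section 7.2:** "patients experiencing clinical deterioration after two doses of pembrolizumab, will be considered treatment failures and will count as tumor progression".

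**The concern.** Response is read from the sum of the index lesions. If one of them is irradiated after baseline and shrinks, the fall in the sum is partly or wholly a radiation effect, yet the definition attributes it to pembrolizumab. Confirmation after 4 weeks does not separate the two causes when the shrinkage lasts that long.

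The trial is single-arm and open-label, and its conclusion rests on a small count of responses. There is no control group in which the same misattribution would appear, and the actual type I error (0.099) leaves almost no room below the 10% allowed. Without a rule set in advance, someone who knows the patient's course would have to decide case by case whether such a response counts.

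**Working it through.** **1. Does the text allow it?** The note in 6.7.2 permits the radiation. Sections 9.0.2.6 and 9.0.2.7 sum all index lesions with no exception. Section 12.0 counts objective responses with no condition on local therapy. Following these sections literally, the irradiated lesion stays in the sum.

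**2. When can it produce an irPR?** Let *s* be the irradiated lesion's share of the baseline SPD, with the other lesions stable and no new measurable lesions. The lesion's area must fall by 0.5/*s*. If both diameters shrink equally, each must fall by 1 − √(1 − 0.5/*s*).

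| Share *s* | Area fall needed | Fall in each diameter |
|---|---|---|
| 100% | 50.0% | 29.3% |
| 80% | 62.5% | 38.8% |
| 60% | 83.3% | 59.2% |
| below 50% | not possible | not possible |

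**3. Reproduce the design (12.0, Table 10).** The inputs are n1 = 20 (continue at 2 or more), n = 39 (reject at 4 or more), p0 = 5% and p1 = 20%. Write b(n, x) for the binomial probability at 5%, with X1 and X2 the responses in stages 1 and 2.

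- Early termination: b(20,0) + b(20,1) = 0.3585 + 0.3774 = 0.736 (stated 0.74).
- Type I error: b(20,2)·P(X2 ≥ 2) + b(20,3)·P(X2 ≥ 1) + P(X1 ≥ 4) = 0.1887 × 0.2453 + 0.0596 × 0.6226 + 0.0159 = 0.0993 (stated 0.099).
- Power, by the same sum at 20%: 0.9165 (stated 91.7%).

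The plan's figures reproduce.

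**4. One radiation-driven response.** Assume exactly one, with the other 38 patients at a true 5%.

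- *In stage 1:* the other 19 stage 1 patients need at least one response, and the other 38 need at least three in total. b(19,1)·P(X2 ≥ 2) + b(19,2)·P(X2 ≥ 1) + P(X1 ≥ 3) = 0.3774 × 0.2453 + 0.1787 × 0.6226 + 0.0665 = **0.270**.
- *In stage 2:* the 20 stage 1 patients must supply two responses themselves, and 18 others remain in stage 2. b(20,2)·P(X2 ≥ 1 of 18) + P(X1 ≥ 3) = 0.1887 × 0.6028 + 0.0755 = **0.189**.

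**5. Dependence on the assumed drug rate.** The same sums at a true 3% give 0.022 with no radiation-driven response, and 0.095 (stage 1) or 0.063 (stage 2) with one.

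**6. How often is one response decisive?** At a true 5%, the chance of passing stage 1 and finishing on exactly three responses is b(20,2)·b(19,1) + b(20,3)·b(19,0) = 0.1887 × 0.3774 + 0.0596 × 0.3774 = 0.094.

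**The case against.** The strongest reply is that other texts already cover the case.

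- **Removal sentence in 6.7.2.** It reaches every listed treatment, and radiation is listed. Read that way, though, it would leave the note with no effect; the natural reading is that the note is the exception. Even on the strict reading, nothing says how the removed patient's response is scored.
- **Section 10.0.1.2.** It moves a patient who starts new anti-cancer therapy to telephone follow-up, and 9.0.1.5.2 lists radiation among cancer treatments. But 10.0.1.2 sits among the post-treatment visits, and 9.0.1.5.3 concerns therapy begun after the last trial dose. The text is ambiguous here and does not close the gap.
- **Section 7.2.** Clinical deterioration is not defined, and one painful lesion need not meet it.

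It is also fair to say that the irRC sections do not instruct anyone to keep an irradiated lesion. They are silent, and the cited criteria, which cannot be consulted here, may address it. That stands, and it is why the point is a gap in the scoring rule, not an error in a stated figure.

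On size, the reply has force. Section 12.0 describes the 5% null as covering chance or some infrequent unknown mechanism, and the mismatch repair-proficient colorectal patients cited in 4.4 had 0 responses in 18, so a true drug rate below 5% is plausible. With a 3% drug rate and 2% of non-responders converted by radiation, the combined rate is 0.03 + 0.97 × 0.02 = 4.94% and the chance of rejection is 9.6%, within the stated limit. A spurious irPR also needs a chain of events: radiation given, a dominant index lesion, enough shrinkage, no offsetting growth and confirmation.

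A reader might also infer an open pre-dose route, because the baseline scan may be 21 days old and exclusion 6 covers only the last 2 weeks. That is mostly closed. The 6.7.2 ban covers Screening, which the flow chart in section 8 sets at days −21 to −1, and exclusion 14 lets the investigator exclude a patient who "Has a history or current evidence of any condition, therapy, or laboratory abnormality that might confound the results of the trial". What remains is radiation after a pre-consent baseline scan, or radiation that the note itself allows during Screening.

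**Conclusion.** The gap is real and should be closed. Followed exactly, the plan can score a radiation effect as an irPR and count it in the primary endpoint. This requires the irradiated index lesion to hold at least half the baseline SPD when the other lesions are stable, and the shrinkage to persist to confirmation.

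The frequency is unknown and probably low. The rise from 9.9% to 27.0% or 18.9% shows what one such response would do at a true rate of 5%. It does not estimate the trial's type I error.

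Two stronger readings are not supported. A reader might infer a large general inflation of type I error, but that needs a conversion rate which the documents do not give, added to a drug rate at the full 5%. A reader might also carry the point over to the comparison by FATSI status, but nothing links on-treatment radiation to FATSI status, and 5.3.2 calls those results exploratory. Confidence is medium, because the wording of 6.7.2 and 10.0.1.2 leaves room for interpretation.

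**What to change.** **Section 9.0.2.7, add:** *Shrinkage of an index lesion irradiated after the baseline scan does not count toward irCR or irPR. From the date of radiation that lesion is removed from both the baseline and follow-up tumor burden when response is assessed; if no index lesion remains, the patient stays in the denominator as a non-responder unless irCR or irPR was confirmed before the radiation.*

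**Section 12.0, add:** report the number of patients irradiated after baseline and, as a sensitivity analysis, IR-ORR with all of them counted as non-responders unless the response was confirmed before the radiation.

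**Section 9.0.2.6, add:** the baseline scan must follow any prior radiation. This closes the small pre-dose residue.

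Removing the lesion, and not the patient, keeps a response seen in unirradiated lesions. The cost is short text, an occasional repeat CT or MRI, and no extra patients. A few patients may lose a genuine response in the irradiated lesion. With one patient forced to non-response and the rest at 20%, exact power is 90.1% if that patient is in stage 1 and 91.4% if in stage 2, against 91.7% as designed. One in each stage gives 89.8%, just under the specified 90%.

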6.8 Rescue Medications & Supportive Care

6.8.1 Supportive Care Guidelines

Subjects should receive appropriate supportive care measures as deemed necessary by the treating investigator. Suggested supportive care measures for the management of adverse events with potential immunologic etiology are outlined below. Where appropriate, these guidelines include the use of oral or intravenous treatment with corticosteroids as well as additional anti-inflammatory agents if symptoms do not improve with administration of corticosteroids. Note that several courses of steroid tapering may be necessary as symptoms may worsen when the steroid dose is decreased. For each disorder, attempts should be made to rule out other causes such as metastatic disease or bacterial or viral infection, which might require additional supportive care. The treatment guidelines are intended to be applied when the investigator determines the events to be related to pembrolizumab.

Note: if after the evaluation the event is determined not to be related, the investigator does not need to follow the treatment guidance (as outlined below). Refer to Section 5.2.1 for dose modification.

It may be necessary to perform conditional procedures such as bronchoscopy, endoscopy, or skin photography as part of evaluation of the event.

- **Pneumonitis:**

- For **Grade 2 events**, treat with systemic corticosteroids. When symptoms improve to Grade 1 or less, steroid taper should be started and continued over no less than 4 weeks.
- For **Grade 3-4 events**, immediately treat with intravenous steroids. Administer additional anti-inflammatory measures, as needed.
- Add prophylactic antibiotics for opportunistic infections in the case of prolonged steroid administration.

- **Diarrhea/Colitis:**

Subjects should be carefully monitored for signs and symptoms of enterocolitis (such as diarrhea, abdominal pain, blood or mucus in stool, with or without fever) and of bowel perforation (such as peritoneal signs and ileus).

- All subjects who experience diarrhea/colitis should be advised to drink liberal quantities of clear fluids. If sufficient oral fluid intake is not feasible, fluid and electrolytes should be substituted via IV infusion. For Grade 2 or higher diarrhea, consider GI consultation and endoscopy to confirm or rule out colitis.
- For **Grade 2 diarrhea/colitis**, administer oral corticosteroids.
- For **Grade 3 or 4 diarrhea/colitis**, treat with intravenous steroids followed by high dose oral steroids.
- When symptoms improve to Grade 1 or less, steroid taper should be started and continued over no less than 4 weeks.

- **Type 1 diabetes mellitus (if new onset, including diabetic ketoacidosis [DKA]) or ≥ Grade 3 Hyperglycemia, if associated with ketosis (ketonuria) or metabolic acidosis (DKA)**
 - For **T1DM** or **Grade 3-4** Hyperglycemia
 - Insulin replacement therapy is recommended for Type I diabetes mellitus and for Grade 3-4 hyperglycemia associated with metabolic acidosis or ketonuria.
 - Evaluate patients with serum glucose and a metabolic panel, urine ketones, glycosylated hemoglobin, and C-peptide.
- **Hypophysitis:**
 - For **Grade 2** events, treat with corticosteroids. When symptoms improve to Grade 1 or less, steroid taper should be started and continued over no less than 4 weeks. Replacement of appropriate hormones may be required as the steroid dose is tapered.
 - For **Grade 3-4** events, treat with an initial dose of IV corticosteroids followed by oral corticosteroids. When symptoms improve to Grade 1 or less, steroid taper should be started and continued over no less than 4 weeks. Replacement of appropriate hormones may be required as the steroid dose is tapered.
- **Hyperthyroidism or Hypothyroidism:**

Thyroid disorders can occur at any time during treatment. Monitor patients for changes in thyroid function (at the start of treatment, periodically during treatment, and as indicated based on clinical evaluation) and for clinical signs and symptoms of thyroid disorders.

 - **Grade 2** hyperthyroidism events (and **Grade 2-4** hypothyroidism):
 - In hyperthyroidism, non-selective beta-blockers (e.g. propranolol) are suggested as initial therapy.
 - In hypothyroidism, thyroid hormone replacement therapy, with levothyroxine or liothyroinine, is indicated per standard of care.
 - **Grade 3-4** hyperthyroidism
 - Treat with an initial dose of IV corticosteroid followed by oral corticosteroids. When symptoms improve to Grade 1 or less, steroid taper should be started and continued over no less than 4 weeks. Replacement of appropriate hormones may be required as the steroid dose is tapered.
- **Hepatic:**
 - For **Grade 2** events, monitor liver function tests more frequently until returned to baseline values (consider weekly).
 - Treat with IV or oral corticosteroids
 - For **Grade 3-4** events, treat with intravenous corticosteroids for 24 to 48 hours.
 - When symptoms improve to Grade 1 or less, a steroid taper should be started and continued over no less than 4 weeks.

- **Renal Failure or Nephritis:**
 - For **Grade 2** events, treat with corticosteroids.
 - For **Grade 3-4** events, treat with systemic corticosteroids.
 - When symptoms improve to Grade 1 or less, steroid taper should be started and continued over no less than 4 weeks.
- **Management of Infusion Reactions:** Signs and symptoms usually develop during or shortly after drug infusion and generally resolve completely within 24 hours of completion of infusion. Table 5 below shows treatment guidelines for subjects who experience an infusion reaction associated with administration of pembrolizumab (MK-3475).

Table 5. Infusion Reaction Treatment Guidelines

NCI CTCAE Grade	Treatment	Premedication at subsequent dosing
Grade 1 Mild reaction; infusion interruption not indicated; intervention not indicated	Increase monitoring of vital signs as medically indicated until the subject is deemed medically stable in the opinion of the investigator.	None
Grade 2 Requires infusion interruption but responds promptly to symptomatic treatment (e.g., antihistamines, NSAIDS, narcotics, IV fluids); prophylactic medications indicated for <=24 hrs	
Stop Infusion and monitor symptoms. Additional appropriate medical therapy may include but is not limited to:
 
 IV fluids Antihistamines NSAIDS Acetaminophen Narcotics 
Increase monitoring of vital signs as medically indicated until the subject is deemed medically stable in the opinion of the investigator. If symptoms resolve within one hour of stopping drug infusion, the infusion may be restarted at 50% of the original infusion rate (e.g., from 100 mL/hr to 50 mL/hr). Otherwise dosing will be held until symptoms resolve and the subject should be premedicated for the next scheduled dose.
 
Subjects who develop Grade 2 toxicity despite adequate premedication should be permanently discontinued from further trial treatment administration.
	
Subject may be premedicated 1.5h (\pm 30 minutes) prior to infusion of pembrolizumab with:Diphenhydramine 50 mg po (or equivalent dose of antihistamine).
 
Acetaminophen 500-1000 mg po (or equivalent dose of antipyretic).

Grades 3 or 4	
Stop Infusion. Additional appropriate medical therapy may include but is not limited to:
 
 IV fluids Antihistamines NSAIDS Acetaminophen Narcotics Oxygen Pressors Corticosteroids Epinephrine 
Increase monitoring of vital signs as medically indicated until the subject is deemed medically stable in the opinion of the investigator. Hospitalization may be indicated.
 
Subject is permanently discontinued from further trial treatment administration.
	No subsequent dosing
Appropriate resuscitation equipment should be available in the room and a physician readily available during the period of drug administration.		

